### 5.8.10. Renal Ultra Sound

Shift tables for renal ultrasound results (“normal”, “abnormal and not clinically significant”, abnormal and clinically significant”) will be presented at each visit.

### 5.8.11. Physical Examination

Since abnormal findings in physical examination need to be reported in AE and vital signs, a data listing of physical examination will be provided.

### 5.8.12. Ataluren Plasma Concentrations

Ataluren plasma concentrations ( $\mu\text{g/mL}$ ) collected prior to the morning dose will be summarized by visit.

## 6. DATA HANDLING

### 6.1. Analysis Visits based on Visit Windows

Since some subjects had early terminations or unscheduled visits in during, the derived analysis visits will be generated by visit window defined as follows. For the 6 weeks post-treatment visit, assign AVISITN=14 and AVISIT=6-Weeks Post-Treatment.

Let Study day=assessment date –first dose date +1.

Study Day	AVISITN	AVISIT
Study Event='SCR' or < study day $\leq$ 1	1	Baseline
1 < study day $\leq$ 126	2	Week 12
126 < study day $\leq$ 210	3	Week 24
210 < study day $\leq$ 294	4	Week 36
294 < study day $\leq$ 378	5	Week 48
378 < study day $\leq$ 462	6	Week 60
462 < study day $\leq$ 546	7	Week 72
546 < study day $\leq$ 630	8	Week 84
630 < study day $\leq$ 714	9	Week 96
714 < study day $\leq$ 798	10	Week 108
798 < study day $\leq$ 882	11	Week 120
882 < study day $\leq$ 966	12	Week 132
966 < study day	13	Week 144

If there are more than 1 valid assessment within one visit window, the last one will be chosen as the analysis value.

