7.2.4. End of Treatment

The patient will return to the clinical research facility at Week 144 (Visit 13) for the End-of-Treatment visit. If the patient discontinues prematurely (ie, before Week 144), and the procedures that would normally be performed at Week 144 should be performed as a Premature-Discontinuation Visit before the patient leaves the study. If the patient terminates the study early because ataluren is commercially available in that country then the patient does not need to come in for the 6-week Post-Treatment Follow-up Visit.

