7.2.5. Post-Treatment Visits

All patients who discontinue study drug, except patients switching to commercial ataluren, must return for a Post-Treatment Visit at the investigator site 6 weeks (± 7 days) after the last dose of study drug and the End of Treatment Visit, for final study-related evaluations. If the End-of-Treatment Visit occurs >6 weeks after the last dose of study drug, the Post-Treatment Visit does not need to be performed.

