Renal findings were seen in mice receiving 1 or 2 doses through 26 weeks of doses of ataluren. A NOAEL for the renal toxicity findings in mice has not been identified; the lowest observed adverse effect level (LOAEL) = 75 mg/kg/day. Exposure in mice at 75 mg/kg/day is 0.3-fold the exposure in patients administered ataluren at the morning, midday, and evening doses of 10, 10 and 20 mg/kg/day, respectively. The renal finding was seen primarily in the distal nephron and involved some degenerative changes (apoptosis) and proliferation of renal epithelium. Renal tubular dilatation and proteinaceous material within the tubules also were seen. The structural integrity of the nephron was maintained, as degenerative/necrotic changes of large numbers of cells were not seen. A few glomeruli in the upper cortex were shrunken but the overall lesion did not primarily involve the glomeruli. The finding was occasionally accompanied by individual increases in serum blood urea nitrogen (BUN) and/or creatinine, however, a dose relationship for these parameters was not observed. The kidney findings were partially to completely reversible as soon as 2 weeks after cessation of dosing. The renal toxicity was observed in mice only, and has not been seen in rats dosed for 24 months or in dogs dosed for 52 weeks despite achievement of exposures in rats and dogs that were comparable to or greater than those observed in mice. In Phase 1 studies in healthy volunteers and Phase 2 studies in patients with DMD and cystic fibrosis, renal laboratory abnormalities have been infrequent.

During the Phase 2b double-blind study of ataluren in nmDMD (PTC124-GD-007-DMD), small increases in mean serum creatinine, BUN, and cystatin C were observed. The values tended to stabilize early in the study and did not increase further with continued treatment.

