### **5.7.2. Laboratory Tests**

Hematological, serum biochemistry, adrenal laboratories, and urine data and their changes (only for continuous laboratory parameters) from baseline will be summarized by visit.

Shift tables for hematology and biochemistry data will also be presented showing change in CTCAE severity grade from baseline to each visit. For parameters for which a CTCAE scale does not exist, shift tables will be presented showing change in results from baseline (normal, low and high [or abnormal]) to each visit (normal, low and high [or abnormal]).

Summary of abnormalities in laboratory variables pre-defined for safety monitoring will be done per the following Table 2.

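### SAP 6.1 files safety and plasma values from an End-of-Treatment visit held more than 6 weeks after last dose under a treatment week

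*SAP*

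**What the plan says.** SAP 6.1 gives the reason for its windows: "Since some subjects had early terminations or unscheduled visits in during, the derived analysis visits will be generated by visit window". The clock starts at first dose: "Let Study day=assessment date –first dose date +1". Windows run from Week 12 to Week 144, and the last has no upper limit. One visit stands outside the day rule: "For the 6 weeks post-treatment visit, assign AVISITN=14". Where several values fall in one window, "If there are more than 1 valid assessment within one visit window, the last one will be chosen as the analysis value". Last dose date is not used in SAP 6.1, and no on-drug cut-off for assessments was found elsewhere in the SAP.

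Protocol 7.2.4 says of a boy who stops early that "the procedures that would normally be performed at Week 144 should be performed as a Premature-Discontinuation Visit before the patient leaves the study". By the schedule of events that includes laboratory tests, vital signs, ECG, a plasma sample, the functional tests, spirometry, the upper-limb assessment (PUL) and renal ultrasound. Protocol 7.2.5 then provides for a late visit: "If the End-of-Treatment Visit occurs >6 weeks after the last dose of study drug, the Post-Treatment Visit does not need to be performed".

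The by-visit displays include the laboratory data (SAP 5.7.2: "urine data and their changes (only for continuous laboratory parameters) from baseline will be summarized by visit", plus shift tables to each visit), vital signs (5.8.1), ECG (5.8.2) and pre-dose plasma concentrations (5.8.12).

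**The concern.** When the End-of-Treatment visit is more than 6 weeks after last dose, the protocol requires no later visit, so it is the boy's only scheduled off-drug assessment. The SAP does not recognise it as off drug. Analysis visit 14 belongs to a differently named visit, so the day rule applies and gives a treatment-week label.

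Laboratory abnormalities are part of the primary endpoint. A value at least 43 days off drug, shown as Week 48 or Week 60, mixes washout with exposure. Protocol 13.2.3 says of the mouse studies: "The kidney findings were partially to completely reversible as soon as 2 weeks after cessation of dosing". A late value could therefore show recovery and be read as no change on treatment, or show a post-treatment change and be read as on treatment. For plasma concentrations the problem is plainer: with a half-life of 2 to 6 hours (protocol 2.2.3), such a sample says nothing about trough exposure. A reader of the by-visit tables could not see that this had happened.

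**Working it through.** **Inputs**
- Window limits, study-day formula and last-value rule: SAP 6.1.
- Late visit: more than 6 weeks after last dose (protocol 7.2.5), so a gap *g* of at least 43 days.
- Scheduled visits: every 12 weeks, ±7 days (protocol Table 3). Week 12*k* is taken as Day 84*k* or 84*k*+1, because the documents do not say which.
- Half-life: 2 to 6 hours (protocol 2.2.3).

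**Step 1: reproduce the SAP's limits.** As midpoints between nominal visits, the upper limits are 84*k* + 42 for *k* = 1 to 11: 126, 210, 294, 378, 462, 546, 630, 714, 798, 882, 966. All 11 match. For *k* = 2 to 11 (Week 24 to Week 132), each window runs from Day 84*k* − 41 to Day 84*k* + 42, which is 84 days.

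**Step 2: label of a late visit.** Let *L* be the study day of last dose; the visit is on Day *L* + *g*. With *g* = 43 and *L* from Day 2 to Day 1009, every such visit gets a treatment-week label and none gets analysis visit 14. The visit shares the last dose's window when *L* + *g* ≤ 84*k* + 42, that is, *L* ≤ 84*k* + 42 − *g*.
- *g* = 43: *L* from 84*k* − 41 to 84*k* − 1, so 41 of 84 days (49%); next window, 43 of 84 (51%).
- *g* = 60: *L* from 84*k* − 41 to 84*k* − 18, so 24 of 84 days (29%); next window, 60 of 84 (71%).

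Example: last dose Day 340 (Week 48 window), visit Day 383. Since 378 < 383 ≤ 462, it is shown as Week 60. In the open-ended Week 144 window, last dose Day 1009 and visit Day 1052 give Week 144.

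**Step 3: when a scheduled on-drug value is replaced.** A scheduled visit on Day *v* must fall on or before last dose and in the same window as the late visit: *v* ≤ *L* ≤ 84*k* + 42 − *g*. The earliest *v* is 84*k* − 7 (or 84*k* − 6).
- *g* = 43: *L* from 84*k* − 7 (or 84*k* − 6) to 84*k* − 1, so 7 (or 6) of 84 days, 8% (or 7%), and only if the visit was held early within its allowance. For Week 48 this is Days 329 (or 330) to 335.
- *g* ≥ 50: the upper limit is 84*k* − 8 or lower, below the earliest *v*, so no days.

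Example: visit Day 330, last dose Day 331, late visit Day 374. Since 294 < 374 ≤ 378, Week 48 shows the Day 374 value. Unscheduled or late on-drug visits could be replaced on other days; they are not counted here.

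**Step 4: time off drug in half-lives.** 43 × 24 / 6 = 172 and 43 × 24 / 2 = 516.

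Steps 2 and 3 count calendar days at an assumed gap. They are not proportions of boys or of values.

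**The case against.** Several points on the other side stand.

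- **Late visits are the exception.** Protocol 7.2.4 places the premature-discontinuation visit before the boy leaves the study, so a gap over 6 weeks should be uncommon. The number is likely small.
- **The protocol does not reclassify the late visit.** It only waives the next one. A reader might infer that SAP 6.1 contradicts the protocol; it does not. The SAP is silent on a case that the protocol foresees.
- **Study-day windows are a legitimate choice for function.** Visit 14 has no 6-minute walk, timed tests, NSAA, PODCI, PUL, spirometry or renal ultrasound. Removing a late visit from the treatment weeks altogether would discard the last such values of boys who stopped, and that loss may be informative. This rules out a blanket exclusion.
- **Other displays limit the harm.** By-patient listings are planned for each CRF module, and the summary of predefined laboratory abnormalities (SAP Table 2) is not stated to be by visit.
- **An off-drug plasma sample might not count as a pre-dose sample.** That is a sensible reading of SAP 5.8.12, but neither 5.8.12 nor the PK population definition says so.

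None of this supplies a last-dose condition for the by-visit safety and plasma tables.

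**Conclusion.** The point holds as a small, specific gap in SAP 6.1. Under the stated rule, laboratory, vital-sign, ECG and plasma values from an End-of-Treatment visit more than 6 weeks after last dose are shown under a treatment week. At a 43-day gap this is the last dose's own window on 41 of 84 last-dose days and the next on 43. It assumes that the rule is programmed as written and that such visits occur. The documents do not give their number, and the impact is minor.

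Three stronger readings are not supported:
- **That about half of late visits overwrite an on-drug value.** The 49% is a share of last-dose days on which the two dates share a window. Replacing a scheduled value is possible on 6 or 7 of 84 days at 43 days and on none from 50.
- **That protocol 7.2.4 and 7.2.5 conflict over who may skip the post-treatment visit.** Both cover boys moving to commercial ataluren. They part only for a boy who leaves because the drug is available and does not take it. Nothing shows that such a boy exists, and the sponsor had already decided to end the study (SAP 5.2).
- **That the 6-week limit on treatment-emergent events is wrong because the post-treatment visit may fall up to 7 days later.** With a half-life of 2 to 6 hours, a 42-day window is defensible.

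**What to change.** Add a rule to SAP 6.1:
- Laboratory, vital-sign and ECG assessments more than 42 days after last dose are labelled post-treatment (analysis visit 14 or a separate off-drug category), shown with days since last dose, and not used in the Week 12 to Week 144 windows.
- Plasma samples taken that late are excluded from the by-visit trough summary in SAP 5.8.12.
- Functional, spirometry, PUL and renal-ultrasound values, which have no Visit 14 counterpart, may stay in their study-day window, flagged as off drug with days since last dose.

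The 42-day cut-off matches the limit the SAP already uses for treatment-emergent events. The cost is a short mapping rule and a flag, with no new data. The downside is that a few boys leave the late treatment-week safety summaries.

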### 6.2. Baseline

In general, Baseline is defined as the last non-missing valid assessment prior to or on the date of the first dose of the study. For spirometry tests, Visit 1 measurements can be used as baseline even if they are after the first dose.

### **6.3. Absolute and Relative Change from Baseline**

The absolute change from baseline at each post-baseline visit is calculated as (post-baseline value – Baseline), while the relative change (%) from baseline at each post-baseline visit is calculated as (post-baseline value – Baseline)/Baseline×100.

### **6.4. Missing Dates of AE and Prior and Concomitant Medications**

#### **6.4.1. Missing Date Information for Adverse Events**

The following imputation rules only apply to cases in which the start date is incomplete (ie, partially missing) for adverse events.

##### **Missing day and month**

- If the year is same as the year of the date of the first dose of double-blind study drug, then the day and month of the date of the first dose of double-blind study drug will be assigned to the missing fields.
- If the year is prior to the year of the date of the first dose double-blind study drug, then December 31 will be assigned to the missing fields.
- If the year is after the year of the date of the first dose double-blind study drug, then January 1 will be assigned to the missing fields.

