8.8. Adverse Event Reporting Period

The first day of adverse event reporting will coincide with the day the first dose of study drug is administered. The adverse event reporting period for this study ends with the 6-week (\pm 7 days) Post-Treatment Visit, except as described in Section 8.7. In addition, SAEs occurring in a patient after the study period should be reported to the sponsor if the investigator becomes aware of them.

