## 5.7. Primary Variables

### 5.7.1. Adverse Events

Adverse events will be classified using MedDRA version 20.1 classification system. The severity of adverse events will be graded by the investigator according to the CTCAE, Version 3.0 whenever possible. A treatment-emergent adverse event (TEAE) is defined as an adverse event that occurs or worsens in the period extending from the day of a subject's first dose of study drug to 6 weeks after the last dose of study drug in this study.

If a subject has multiple events under any given SOC and PT, the subject will be counted only once under that SOC and PT. If a subject has the same AE on multiple occasions, the highest severity (fatal, life-threatening, severe, moderate, and mild) recorded for the event will be presented and the highest drug relationship (1 = 'Unrelated', 2 = 'Unlikely', 3 = 'Possibly', 4 = 'Probably', 5 = 'Related'), reclassified into Related ('Possibly Related', 'Probably Related', 'Related') or Not Related ('Unrelated' and 'Unlikely'), will be presented on the respective tables.

Total numbers of AEs, TEAEs and serious AEs (SAE) and the number and percentage of subjects experiencing  $\geq 1$  TEAE,  $\geq 1$  SAE, discontinuation due to AE, and death will be tabulated. The number and percentage of subjects with TEAEs and SAEs will be by relationship to study drug and CTCAE/severity, respectively.

The number and percentage of subjects experiencing a specific TEAE will be tabulated

- 1) by SOC, and PT
- 2) by SOC, PT, and CTCAE/severity grade
- 3) by SOC in the descending order of the SOC frequency overall group,
- 4) by PT in the descending order of the PT frequency in overall group.

The following TEAEs will be analyzed similarly:

- 1) by SOC, and PT and

- 2) by SOC, PT, and CTCAE/severity grade.
- Possibly or probably treatment-related TEAEs
  - Serious TEAEs and possibly or probably treatment-related serious TEAEs
  - TEAEs leading to discontinuation from treatment
  - Adrenal, hepatic and renal events leading to special diagnostic evaluations TEAEs and possibly or probably treatment-related hepatic and renal TEAEs leading to special diagnosis evaluation
  - TEAEs with CTCAE/severity grade  $\geq 3$  and possibly or probably treatment-related TEAEs with CTCAE/severity grade  $\geq 3$
  - Common TEAEs (subject frequency of  $\geq 5\%$ )

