##### **Missing day only**

- If the month and year are same as the year and month of the date of the first dose double-blind study drug, then the date of the first dose double-blind study drug will be assigned to the missing day.
- If either the year is before the year of the date of the first dose of double-blind study drug or if both years are the same but the month is before the month of the date of the first dose of double-blind study drug, then the last day of the month will be assigned to the missing day.
- If either the year is after the year of the date of the first dose of double-blind study drug or if both years are the same but the month is after the month of the date of the first dose of double-blind study drug, then the first day of the month will be assigned to the missing day.

If the stop date is complete and the imputed start date as above is after the stop date, the start date will be imputed by the stop date.

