##### **Missing day and month**

- If the year of the incomplete stop date is the same as the year of the date of the last dose of double-blind study drug, then the day and month of the date of the last dose of double-blind study drug will be assigned to the missing fields.
- If the year of the incomplete stop date is prior to the year of the date of the last dose of double-blind study drug, then December 31 will be assigned to the missing fields.

- If the year of the incomplete stop date is after the year of the date of the last dose of double-blind study drug, then January 1 will be assigned to the missing fields.

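### Partial adverse-event dates are imputed against the first double-blind dose of Study 020, so some on-treatment events in 020e are dated before treatment and drop out of the TEAE tables

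*SAP*

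**What the plan says.** SAP 6.4.1 gives rules for adverse events whose start date is partly missing: "The following imputation rules only apply to cases in which the start date is incomplete". Every branch compares the recorded year or month with the first dose of double-blind drug.

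- **Month and day missing, same year as that dose:** "the day and month of the date of the first dose of double-blind study drug will be assigned to the missing fields".
- **Month and day missing, later year:** "If the year is after the year of the date of the first dose double-blind study drug, then January 1 will be assigned".
- **Day missing, later month:** "then the first day of the month will be assigned to the missing day".

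One correction follows. It applies only where "If the stop date is complete and the imputed start date as above is after the stop date", and it then moves the start back to the stop date.

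SAP 5.7.1 defines a treatment-emergent event by a window running from the "first dose of study drug to 6 weeks after the last dose of study drug in this study". Protocol 8.8 opens adverse-event collection at the same point: "The first day of adverse event reporting will coincide with the day the first dose of study drug is administered".

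SAP 6.4.2.1 uses the same first double-blind dose for medication start dates. SAP 6.4.2.2 ties incomplete medication stop dates to the last double-blind dose, for example when the stop year is "the same as the year of the date of the last dose of double-blind study drug".

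**The concern.** There is no double-blind drug in 020e. SAP Section 2 reserves that term for PTC124-GD-020-DMD, which has a planned treatment duration of 48 weeks (Protocol 13.2.2). The imputation anchor and the start of the TEAE window are therefore about 48 weeks apart.

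Imputation rules of this kind protect against losing events. If the partial date could fall on or after first dose, the event is assigned the first-dose date and counted. Here that protection is attached to a dose in another study and never acts on the 020e dose. Because 020e collects adverse events only from its own first dose, a partial date in the entry year or month should in most cases be an on-treatment event.

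The TEAE tables are the core of the primary analysis: by system organ class and preferred term, severity, relatedness, seriousness and discontinuation. The exposure-adjusted rates would lose these events from the numerator while keeping all days on drug in the denominator. For medications, corticosteroid use during the study (a specified summary in SAP 5.5) would be shortened.

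**Working it through.** The plan gives no figure for this rule, so there is nothing to reproduce. The check applies the rule as written.

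**Inputs**

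- First patient dosed in Study 020: 10 April 2013 (Protocol 1.1).
- Recruitment to Study 020: about 18 months (Protocol 1.1), taken as 550 consecutive first-dose dates *D*, 10 April 2013 to 11 October 2014.
- First 020e dose *E* = *D* + 337 days: 48 weeks plus one day, since Protocol 7.2.1 aims for Day 2 of the Week 48 visit. Gaps of 336 to 357 days were also tried (assumed range).
- Treatment in 020e: up to 144 weeks = 1,008 days (Protocol 6.2.1). The TEAE window adds 6 weeks = 42 days. Because the sponsor ended the study early (SAP 5.2 and 7), 48 weeks = 336 days is used as a short-follow-up assumption.

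**Rule, with anchor *r***

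- Year only, recorded year *y*: *r* if *y* is the year of *r*; 31 December if earlier; 1 January if later.
- Day missing: *r* if the month matches *r*; last day of the month if earlier; first day if later.
- The event loses TEAE status when the imputed date is before *E*.

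**Worked case.** *D* = 10 April 2013 gives *E* = 13 March 2014. An on-treatment event recorded only as 2014 is imputed to 1 January 2014. One recorded as March 2014 is imputed to 1 March 2014. Both precede *E*, so neither is a TEAE. With *r* = *E*, both become 13 March 2014 and are counted.

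**All 550 entry dates, onset in the 020e start year or month**

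| Partial date | Imputed before *E*, anchor *D* | Anchor *E* |
|---|---|---|
| Year only, start year | 549/550 (99.8%) | 0/550 |
| Day missing, start month | 532/550 (96.7%) | 0/550 |

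The exceptions are an *E* on 1 January (1 date) and an *E* on the first of a month (550 − 532 = 18 dates). Where *D* and *E* share a calendar year, a year-only event is set to *D*, which is also before *E*. Onsets in later years, or day-missing onsets in later months, are unaffected.

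**Share of partial-date events lost, onsets spread evenly.** Averaged over entry dates, about 188.7 on-treatment days fall in an affected start year and about 14.7 in an affected start month.

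| Follow-up | Year only | Day missing |
|---|---|---|
| 144 weeks on drug | 188.7/1,008 = 18.7% | 14.7/1,008 = 1.5% |
| plus 6 weeks | 188.7/1,050 = 18.0% | 14.7/1,050 = 1.4% |
| 48 weeks on drug | 188.7/336 = 56% | 14.7/336 = 4.4% |
| plus 6 weeks | 188.7/378 = 50% | 14.7/378 = 3.9% |

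For gaps of 336 to 357 days, the 144-week on-drug shares run from 18.1% to 18.8% (year only) and stay at 1.5% (day missing).

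**Medication stop dates.** Suppose the last double-blind dose is in March 2014. A corticosteroid stopped in October 2014 but recorded only as 2014 is given that March date, at or about 020e entry. A year-only stop in a later year becomes 1 January of that year. With the last 020e dose as anchor, stops in years before that dose would go to 31 December.

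**The case against.** The strongest reply is that the wording is left over from a double-blind template and was never meant to point at Study 020. The text supports this. SAP 6.4.2.2 provides for a missing last double-blind dose in a subject who is still on-going, yet entry to 020e requires completed 020 treatment, so that provision makes sense only for the current study's drug. SAP 6.4.2 also mentions rescue medications, which 020e does not define. Elsewhere the SAP works from this study's first dose, and a programmer who quietly did the same would lose nothing.

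The reach is also limited. An event in the start year with a known later month stays a TEAE. Affected events remain in the total adverse-event count and the by-patient listings. Deaths, serious events, and events leading to discontinuation have listings not restricted to TEAEs. The 549/550 and 532/550 figures count entry dates, not events. Onset date is a required item (Protocol 8.3), so partial dates may be few. Some may be true earlier onsets.

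These limits on size and reach stand. They do not repair the rule. The SAP never says that the phrase means 020e drug, it declares that it overrides the protocol where they conflict, and Version 2 left the wording in place. No rule keeps an event as a TEAE when its partial date is compatible with onset on treatment, and the single correction in 6.4.1 can only move a start earlier.

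**Conclusion.** The concern holds: the rule is wrong as written. In the two affected situations it places on-treatment events before the first 020e dose for nearly every entry date. It errs in one direction only, towards fewer TEAEs.

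The expected loss is about 18-19% of year-only events and 1.5% of day-missing events over 144 weeks, rising to 50-56% and about 4% at 48 weeks. These shares assume evenly spread onsets, a 336- to 357-day gap between first doses, and Study 020 entry over about 18 months. They are fractions of an unknown number of partial dates, so the effect on the tables cannot be stated and may be slight. The shortening of recorded corticosteroid use has the same cause and was not quantified. Because the rule determines what counts in the primary safety tables, it should be corrected whichever way the phrase was meant.

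**What to change.** In SAP 6.4.1 and 6.4.2.1, replace each reference to the first double-blind dose with the first dose of study drug in Study 020e. In 6.4.2.2, replace each reference to the last double-blind dose with the last dose of study drug in Study 020e. As a safeguard, add a sentence that an adverse event counts as treatment-emergent unless the recorded part of its start date shows onset before the first 020e dose.

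The cost is a short SAP amendment, one change to the date-imputation macro, and a rerun of the affected tables. TEAE counts may rise slightly. If the programs already use the 020e dates, only the wording changes. Reporting the number of events with partial start dates would let readers see how much depended on the rule.
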